3.2.4 Starting Dose and Dose Escalation Plan

Enrollment of subjects at each DL proceeds based on the Keyboard design outlined in the Appendix Section 16.3. Dose escalation will begin on Schedule 1 at the starting dose of 0.0001 mg/kg as outlined in Table 5 below; intermediate DLs not shown may be explored based on emerging data (e.g., safety). As it is likely that the dose of 0.0001 mg/kg will result in minimal to no biologic activity, escalations for the first two DLs will proceed in log increments. Beyond DL2,

escalations will not exceed half-log increments. Doses beyond the maximum dose stated in the protocol may be explored if the MTD has not been reached. An MTD or MAD may be determined on Schedule 1 or Schedule 2 and up to 10 or more dose levels may be explored if safety allows.

Table 5: SL-279252 Dose Escalation Plan

Dose Level	Dose of SL-279252 (mg/kg) ^{a,b,c,d}	Duration of Infusion ^e
Level 1	0.0001 mg/kg	5-30 minutes
Level 2	0.001 mg/kg	5-30 minutes
Level 3	0.003 mg/kg	5-30 minutes
Level 4	0.01 mg/kg	30 minutes (+/- 10 minutes)
Level 5	0.03 mg/kg	30 minutes (+/- 10 minutes)
Level 6	0.1 mg/kg	30 minutes (+/- 10 minutes)
Level 7	0.3 mg/kg	30 minutes (+/- 10 minutes)
Level 8	1.0 mg/kg	1 hour (+/- 15 minutes)
Level 9	3.0 mg/kg	1 hour (+/- 15 minutes)
Level 10	6.0 mg/kg	1 hour (+/- 15 minutes)

a) **Dose escalation begins on Schedule 1:** SL-279252 may be administered in the first cycle on days 1, 8, and 15 of the first 28-day cycle and then once every 2 weeks on days 1 and 15 of each 28-day cycle beginning at cycle 2.

b) **Dose escalation on Schedule 2 may be tested:** If Schedule 2 is opened, SL-279252 may be administered once weekly on days 1, 8, 15, and 22 of each 28-day cycle. The starting dose on schedule 2 will be at least one dose level below the current Schedule 1 dose level defined by the Keyboard design. If Schedule 2 is opened for enrollment, then enrollment on Schedule 1 will be halted.

c) Intermediate dose levels may be tested based on emerging safety data. The option to explore more than 10 dose levels on Schedule 1 or additional dose levels on Schedule 2 is also a possibility if safety allows. Escalations will not exceed half-log increments after dose level 2.

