A minimum of 3 subjects will be evaluated in each DL during dose escalation on Schedule 2. A minimum 3-day stagger between dosing the first and second subject at the same DL is required, although this mandate may change based on emerging safety data. The incidence of DLT will be assessed over a period of 28 days during the first cycle of therapy (DLTs are defined in Section [3.2.6](#)) on Schedule 2.

Evaluation of a Less Frequent Dosing Schedule: If safety and pharmacodynamic data from Schedule 1 support exploration of a less intensive dosing schedule, then cohort enrollment on this as yet to be identified schedule will be instituted in lieu of Schedule 1. For example, SL-279252 may be administered once every two weeks in every cycle including the first cycle or once every 21 or 28 days. The starting dose on this less intensive schedule would be instituted at the current Schedule 1 dose level defined by the Keyboard design or a lower dose level based on emerging safety data.

3.2.5 Criteria for Expanding a Single Subject Cohort in Schedule 1

Dose escalation on Schedule 1 allows enrollment of a single subject (minimum of one subject per DL) into dose levels 1 to 5 unless a Grade ≥ 2 toxicity or DLT (Section [3.2.6](#)) is observed over the 21-day DLT assessment period with the exceptions listed below. A qualifying event of Grade ≥ 2 toxicity or DLT will trigger a switch to enrollment of ≥ 3 subjects for DLT assessment in that specific dose level and each DL thereafter.

Toxicity exceptions that will not trigger a switch to enrollment of ≥ 3 subjects:

- Grade 2 fatigue
- Grade 2 nausea and vomiting controllable with anti-emetics within 72 hours
- Vitiligo and alopecia of any Grade
- Grade 2 IRR that can be managed with premedication and/or change in infusion duration
- Grade 2 hematologic abnormalities not associated with clinical signs/symptoms
- Grade 2 electrolyte abnormalities that are not associated with clinical signs/symptoms
- Grade 2 amylase and lipase without evidence of clinical symptoms of pancreatitis
- Toxicities related to disease progression or intercurrent illness, inflammatory reactions related to local tumor response such as severe pain

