9. STATISTICAL CONSIDERATIONS

9.1 Description of Statistical Methods

The study has 2 parts: dose escalation and dose expansion. During dose escalation, the primary objective is to evaluate the safety and tolerability of SL-279252 and to identify the MTD or MAD of SL-279252 in participants with locally advanced or metastatic select malignancies. Schedule 1 will be evaluated first, with dose escalation following the Keyboard design with a target DLT rate of 30% (acceptable range of 25-33.3%). Ten DLs are planned with a planned maximum sample size of 42 subjects. Single subject cohorts may initially be enrolled until the subject in a single subject cohort experiences a qualifying \geq Grade 2 toxicity (see Sections 3.2.5 and 3.2.6) or a DLT **OR** DL 6 is reached. Subsequently, cohorts of at least 3 subjects will be enrolled. The full dose escalation rules are outlined in Appendix Section 16.3. The Sponsor, in consultation with the SMC, may decide to stop enrollment in Schedule 1 early (e.g., based on safety, pharmacodynamics) and begin enrollment in Schedule 2 (see Section 3.2.7). If Schedule 2 is opened, dose escalation will also follow the Keyboard design with the same target DLT rate of 30%. We anticipate that 4 DLs will be evaluated in Schedule 2 with a planned maximum sample size of 15 subjects. All cohorts will enroll at least 3 subjects in Schedule 2 (see full dose escalation rules in Appendix Section 16.3). **NOTE:** If Schedule 2 is opened, the Sponsor may also elect to stop enrollment in schedule 2 early (e.g., based on safety) and resume enrollment in Schedule 1. If both schedules are evaluated, the MTD or MAD may be determined for each schedule (denoted MTD1/MAD1 and MTD2/MAD2). The MTD(s) will be determined using isotonic regression based on DLTs observed during dose escalation (see Section 9.2.1). A MAD will be reported if a schedule is fully evaluated, but the DLT rate never reaches the target range of 25-33.3%.

During the dose escalation additional subjects (approximately 6) may be enrolled into a pharmacodynamic cohort to obtain additional pharmacodynamic data at select dose levels that have previously completed evaluation for safety and not exceeded the MTD.

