9.2.1.2 Simulations for Schedule 2 (assuming 4 dose levels)

The simulations assume the following:

- Subjects are enrolled in cohorts of 3 (i.e., dose escalation decisions are made after each subject is evaluated)
- Maximum sample size = 15

	Dose 1	Dose 2	Dose 3	Dose 4	Number of Subjects	% Early Stopping
Scenario 1						
True DLT rate	0.3	0.47	0.55	0.64		
Selection %	64.36	18.02	4.06	0.26		13.3
# subjects treated	8.84	3.62	0.56	0.04	13.1	
Scenario 2						
True DLT rate	0.11	0.3	0.45	0.67		
Selection %	23.82	49.9	24.04	1.94		0.3
# subjects treated	5.66	6.44	2.48	0.28	14.9	
Scenario 3						
True DLT rate	0.02	0.13	0.3	0.47		
Selection %	1.18	24.46	54.24	20.12		0
# subjects treated	3.42	5.23	4.83	1.51	15	
Scenario 4						
True DLT rate	0.05	0.1	0.15	0.3		
Selection %	1.34	8.58	38.22	51.84		0.02
# subjects treated	3.66	4.25	4.15	2.93	15	

For Schedule 2, with a maximum of 15 subjects, the chance of selecting the true MTD is at least 40% for a range of possible scenarios. Only 3 subject cohorts were considered for Schedule 2.

If both Schedule 1 and 2 are evaluated, the planned maximum total sample size during dose escalation process is 57 subjects. If only Schedule 1 is evaluated (which is expected), the planned maximum total sample size during dose escalation is 42 subjects. The final sample size will depend on whether dose escalation is stopped early (as outlined in Appendix Section 16.3), whether 1 or 2 schedules are evaluated, and whether any revisions are needed to the maximum sample sizes.

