9.3 Populations for Analyses

For the analysis, the following populations are defined:

Population	Description
Enrolled	All subjects who sign the main study ICF.
Screen Failures	A subject who signs the informed consent but has not received any dose of SL-279252
All Treated	All subjects who receive at least one dose of SL-279252. Safety data will be evaluated based on this population.
DLT Evaluatable	All subjects in the All Treated population who receive at least 2 doses of SL-279252 for Schedule 1 or at least 3 doses for Schedule 2, complete the safety follow up through DLT evaluation period or experience any DLT during the DLT evaluation period. The DLT evaluation period is defined as the first 21 days or 28 days of treatment on Schedule 1 or Schedule 2, respectively. Evaluatable subjects will be used to guide dose escalation and to determine the MTD or MAD.
Evaluatable for Efficacy	A subject who received at least 3 doses of SL-279252 and had at least one post-baseline disease assessment or had progressed or died before the first post-baseline disease assessment. .
Pharmacokinetic	All subjects in the All Treated population who received at least one dose of SL-279252 and have at least one evaluable post-dose sample collected. The PK population will be used for PK analysis.
Pharmacodynamic	All subjects in the All Treated population for whom sufficient samples are available for the analysis. The pharmacodynamic population will be used for the pharmacodynamic data analysis.

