- The column corresponding to the total number of evaluable subjects treated at the current dose level should be used to make the appropriate decision (i.e., escalate, stay at the same dose, de-escalate or eliminate).
- If a subject is not evaluable, a decision can still be made based on the total number of subjects who are evaluable at the current dose without enrolling an additional subject (unless all subjects in a cohort are not evaluable*).

More than 3 subjects may be enrolled in a cohort if additional subject(s) are available for dosing after consultation with the Sponsor.

***NOTE:** If all subjects in a cohort are not evaluable, an additional cohort should be enrolled at the same dose level.

Dose escalation for schedule 2 may continue until:

[figure not shown]
- The trial is stopped for safety **OR**
- The maximum sample size of 15 subjects is reached **OR**
- The maximum sample size has not been reached but 12 subjects have been enrolled at the current dose level **OR**
- The Sponsor, in consultation with the SMC, decides to stop enrollment in schedule 2 early (based on safety.) and resume enrollment in schedule 1 or begin enrollment in dose expansion*

*At least 6 subjects will be enrolled at the dose level to be used during dose expansion and sufficient safety follow-up completed to confirm safety and tolerability (as determined by the SMC) before a decision can be made to begin dose expansion early.

NOTE: The maximum sample size of 15 may be revised if additional dose levels are evaluated or if more additional subjects (i.e., subjects available for dosing beyond the number required in a cohort) are enrolled than anticipated. The Sponsor, in consultation with the SMC, may also elect to add subjects if additional safety data are needed to select a dose and schedule for the expansion cohorts.

16.3.1.3 Keyboard Design Scenarios – Schedule 1

Scenario #1:

[figure not shown]

NOTE: All subjects in Scenario #1 are evaluable.

1. Subject #1 is enrolled at Dose Level 1 in a single subject cohort. Subject #1 does not experience a DLT or a \geq Grade 2 toxicity, so dose escalation is allowed and Subject #2 is enrolled at Dose Level 2 in a single subject cohort.
2. Subject #2 does not experience a DLT or a \geq Grade 2 toxicity, so dose escalation is allowed and Subject #3 is enrolled at Dose Level 3 in a single subject cohort.

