6. One (1) subject enrolled at Dose Level 6 is not evaluable and 0 of the other 2 subjects enrolled at Dose Level 6 experience a DLT. Following the table in Section 16.3.1 (looking at the column for 2 evaluable subjects treated at the current dose), dose escalation is allowed and the next 3 subjects (Subjects #9, #10 and #11) are enrolled at Dose Level 7.

7. One (1) of the 3 subjects enrolled at Dose Level 7 experience a DLT, so following the table in Section 16.3.1, the next 3 subjects (Subjects #12, #13 and #14) are also enrolled at Dose Level 7.
8. Of the 6 total subjects enrolled at Dose Level 7, 1 subject is not evaluable and only 1 of the other 5 subjects experience a DLT. Following the table in Section 16.3.1 (looking at the column for 5 evaluable subjects treated at the current dose), dose escalation is allowed and the next 3 subjects (Subjects #15, #16 and #17) are enrolled at Dose Level 8.
9. Two (2) of the 3 subjects enrolled at Dose Level 8 experience a DLT, so following the table in Section 16.3.1, de-escalation is required and the next 3 subjects (Subjects #18, #19 and #20) are enrolled at Dose Level 7. An additional subject was available for treatment (Subject #21), so was included in the cohort as well (i.e., 4 subjects are enrolled at Dose Level 7).
10. Of the 10 total subjects enrolled in Dose Level 7, 1 subject is not evaluable and only 1 of the other 9 subjects experience a DLT. Following the table in Section 16.3.1 (looking at the column for 9 evaluable subjects treated at the current dose), dose escalation is allowed and the next 3 subjects (Subjects #22, #23 and #24) are enrolled at Dose Level 8.
11. Four (4) of the 6 total subjects enrolled at Dose Level 8 experience a DLT, so following the table in Section 16.3.1, Dose Level 8 is eliminated from the trial. This means that subjects will no longer be enrolled in Dose Level 8, 9 or 10. De-escalation is required and the next 3 subjects (Subjects #25, #26 and #27) are enrolled at Dose Level 7.
12. The maximum sample size of 42 subjects has not been reached, but 12 subjects have now been enrolled at Dose Level 7, so dose escalation can stop early and the MTD can be determined based on the 27 subjects enrolled.

Scenario #4:

1. Subject #1 is enrolled at Dose Level 1 in a single subject cohort. Subject #1 is not evaluable. Because the one subject enrolled at the dose level is not evaluable, another subject (Subject #2), is enrolled at Dose Level 1 in a single subject cohort.

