16.3.1.4 Keyboard Design Scenarios – Schedule 2

If schedule 2 is opened, the table in Section 16.3.1 will be used for all dose escalation decisions and the same principles demonstrated in Scenarios #1-4 apply with the following exceptions:

1. All cohorts will include at least 3 subjects (there are no single subject cohorts).
2. Because there are no single subject cohorts, \geq Grade 2 toxicities do not guide dose escalation.
3. The maximum total sample size is 15 subjects.

Reference:

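### Does letting Schedule 2 escalate on fewer than three evaluable subjects contradict the stated minimum of three, or undo the 40% selection claim?

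*Protocol*

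**What the plan says.** Protocol Section 3.2.4 states: "A minimum of 3 subjects will be evaluated in each DL during dose escalation on Schedule 2". SAP Section 3.2 repeats the sentence.

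Protocol Section 16.3.1.2 sets the rule for lost subjects. A decision "can still be made based on the total number of subjects who are evaluable at the current dose without enrolling an additional subject", and a further cohort is required only when nobody in the cohort is evaluable. The decision table in Section 16.3.1 (SAP Table 1) has columns for one and two evaluable subjects; in both, zero DLTs means escalate and one means de-escalate. Step 6 of Scenario 3, a Schedule 1 example, applies this to a cohort that lost one subject: "looking at the column for 2 evaluable subjects treated at the current dose), dose escalation is allowed". For Schedule 2, Section 16.3.1.4 says "the same principles demonstrated in Scenarios #1-4 apply with the following exceptions", and none of the three exceptions concerns evaluability.

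Section 3.2.4 opens with "Enrollment of subjects at each DL proceeds based on the Keyboard design" and points to Section 16.3. Section 9.1 says "All cohorts will enroll at least 3 subjects in Schedule 2" and also refers to Section 16.3 for the full rules.

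Section 9.2.1.2 reports simulations with cohorts of three, a maximum of 15 subjects and four scenarios, and concludes that the true MTD is selected at least 40% of the time. It adds: "Only 3 subject cohorts were considered for Schedule 2". No non-evaluable rate is mentioned there or in Section 9.2.1.

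**The concern.** Taken literally, the sections give different answers to the same data. After two evaluable subjects with no DLT, Section 16.3.1.2 escalates, while Section 3.2.4 and SAP Section 3.2 appear to want a third result first. Fewer subjects give a weaker filter: a dose that is too toxic passes more easily on two clean results than on three.

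The 40% claim also looks exposed. It was simulated without stated losses, while the protocol plainly expects some, since it writes rules and worked examples for them. If losses were common, the advertised chance of finding the MTD might not be the one delivered.

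A smaller worry is attached. SAP Section 3.2 lets the escalation decision be made once the first three subjects clear the DLT window when more were accrued for reasons other than toxicity. It does not say how a later subject's DLT counts, whereas the table uses all evaluable subjects at the dose.

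**Working it through.** **Wording.** The contradiction needs *evaluated* to mean DLT Evaluable, a term Section 9.3 defines and Section 3.2.4 does not use. Elsewhere the documents use *evaluated* for enrolled or treated:

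- Section 3.3.1 has up to 15 subjects evaluated per expansion cohort; Section 3.1.2 has up to 15 enrolling.
- SAP Section 3.3 wants six evaluated before expansion; protocol Section 9.2.1 wants six treated.
- For the Schedule 2 minimum itself, Section 9.1 says enroll, Section 16.3.1.2 says enrolled in cohorts of three, and Section 16.3.1.4 says cohorts include at least three.

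In place, the sentence in Section 3.2.4 contrasts Schedule 2 with the single-subject cohorts just described for Schedule 1.

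**One decision.** With true DLT rate p and k evaluable subjects at a new dose, the table escalates with probability (1−p)^k for k = 1, 2, 3. At p = 0.47: 0.53³ = 0.149, 0.53² = 0.281, 0.53 = 0.530.

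For a whole cohort of three with loss rate q independent of DLT, given at least one evaluable, the chance is [(q + (1−q)(1−p))³ − q³] / (1 − q³). At q = 0.05, 0.15, 0.30 this is 0.169, 0.214, 0.283, against 0.149 with no loss. If every DLT is captured before loss, it stays at 0.149, 0.148, 0.145.

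The small columns are also stricter in the other direction. One DLT in three means stay; one in two means de-escalate. At p = 0.47 the chance of de-escalating is 1 − 0.281 = 0.719 on two subjects, against 3(0.47²)(0.53) + 0.47³ = 0.455 on three.

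**Whole trial.** Simulation with the printed table, cohorts of three, cap 15, stop at 12 per dose, isotonic selection at 0.30, 60,000 runs per setting. Loss rates are assumed. Correct selection (%):

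| Setting | Sc 1 | Sc 2 | Sc 3 | Sc 4 |
|---|---|---|---|---|
| Protocol 9.2.1.2 | 64.4 | 49.9 | 54.2 | 51.8 |
| No loss | 65.4 | 50.6 | 53.3 | 51.0 |
| Rule as written, independent loss 15% | 65.7 | 49.6 | 48.7 | 46.4 |
| same, 30% | 64.4 | 47.3 | 44.9 | 44.4 |
| Rule as written, only DLT-free subjects lost, 15% | 68.3 | 48.9 | 47.6 | 39.8 |
| same, 20% | 68.2 | 47.8 | 44.9 | 36.2 |
| same, 30% | 67.4 | 44.2 | 39.8 | 30.2 |
| Three evaluable required inside cap, independent loss 15% | 65.6 | 51.6 | 50.1 | 42.8 |
| same, 30% | 66.5 | 50.2 | 49.6 | 25.8 |

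The plan's figures therefore reproduce with everyone evaluable. A separate 20,000-run simulation also matched them within 2 points.

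Mean subjects treated above the MTD in Scenarios 1 to 3 are 4.13, 2.71, 1.48 with no loss and 4.13, 2.77, 1.55 at 15% independent loss under the written rule. The protocol's own table gives 3.62 + 0.56 + 0.04 = 4.22, 2.48 + 0.28 = 2.76, and 1.51.

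**Does requiring three evaluable rescue Scenario 4?** Not inside the cap, as the table shows. With replacement until three are evaluable and a cap that counts only evaluable subjects (20,000 runs), it stays near 51% under independent loss. When only DLT-free subjects are lost it still falls to 45.7, 40.2 and 32.8% at 10, 20 and 30%, with mean enrolment of 16.4, 18.1 and 20.3. Selective loss drives the fall, not the minimum.

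**SAP first-three sentence.** The chance of 0/3 followed by a full count that does not say escalate, with 4, 5 or 6 accrued, is (1−p)³ times p, p², or P(at least 2 DLTs in 3). At p = 0.47: 0.070, 0.033, 0.068. At p = 0.30: 0.103, 0.031, 0.074. These matter only if a later DLT were ignored, which the sentence does not say.

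**The case for a change.** The best case for a change is that an escalation rule in a first-in-human study should not depend on which section is read. Section 3.2.4 speaks of enrolling three or more for Schedule 1 and then of evaluating three for Schedule 2, so the verb changes within one section. The SAP repeats *evaluated* and does not reproduce the no-replacement rule beside its table, so a reader of the SAP alone sees only the minimum.

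Losses are also foreseeable. Section 9.3 asks for at least three doses and 28 days on Schedule 2, against two doses and 21 days on Schedule 1. A subject counts either way on having to "complete the safety follow up through DLT evaluation period or experience any DLT during the DLT evaluation period", so DLTs are kept while DLT-free subjects can be lost, which is the unfavourable pattern above. At an assumed 10% loss, 11 to 50% of simulated trials escalate at least once on fewer than three evaluable subjects, depending on scenario and loss pattern.

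Some of this stands. The wording is loose, and the 40% claim is silent on losses. But SAP Section 12 lists its departures from the protocol and none touches the escalation rule, so the SAP is not setting a rival one. The protocol's rule for lost subjects is explicit, tabulated and illustrated on two evaluable subjects. Section 16.3.1.2 also says the 15 may be revised and that the Sponsor, with the SMC, may add subjects if more safety data are needed, so a badly depleted cohort need not be left as it is.

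**Conclusion.** No change to the plan follows. The apparent conflict is one loosely used verb. A team that follows the section the protocol itself names for escalation has a complete rule, and aligning the verb would alter no result. Which minimum is clinically preferable is not judged here.

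The 40% claim is not refuted. Under the rule as written, the lowest scenario stays at 44% with 30% loss unrelated to DLT, and mean exposure above the MTD moves by at most 0.07 subjects at 15%. The claim fails clearly only in Scenario 4, the one with the MTD at the top dose: 36% at 20% and 30% at 30% loss confined to DLT-free subjects, with 15% on the line at 39.8%. The documents give no loss rate, so these are what-if figures.

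A firm three-evaluable minimum would be a trade-off. It costs selection accuracy in Scenario 4 inside the cap of 15, or extra subjects outside it, and it does not remove the effect of selective loss. A run with losses would be an optional sensitivity check for a schedule that Section 9.2.1.2 does not expect to be needed. The SAP's first-three sentence is permissive and does not say an observed DLT may be disregarded, so it can be applied consistently with the all-evaluable table.
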